We will measure blood and lung lavage cathelicidin levels in 20 vitamin D insufficient individuals (10 participants with serum 25-OH Vitamin D<10 ng/ml and 10 participants with serum 25-OH vitamin D between 10-20) before and after eight weeks of oral vitamin D supplementation to determine the effect of vitamin D supplementation on cathelicidin levels. Completion of this project directly or indirectly works towards ultimately understanding if a readily measurable blood marker, cathelicidin, can inform who may benefit from vitamin D supplementation to prevent chronic lung disease. The results from this application would lead to a therapeutic intervention study that will provide further opportunities to improve our understanding of the relationship between vitamin D, cathelicidin and lung function.

1.3 Objectives:

To evaluate the effect of oral vitamin D supplementation on plasma and lung cathelicidin measures in individuals with vitamin D insufficiency. Our primary analysis will include comparison between pre- and post-supplementation cathelicidin levels using paired t-tests for repeated measures

1.4 Overall Project Design:

The design of the study to complete this aim will be in the format of a baseline and repeat bronchoscopy after oral supplementation with 50,000 IU vitamin D3 weekly for eight weeks in individuals with reduced vitamin D levels. The specific study data collection is outlined in the table below.

- Participants will undergo a screening assessment (visit S0) to determine the presence of vitamin D insufficiency (serum 25OH-VitD <20 ng/ml) as well as normal renal function and calcium levels. Pre- and post-bronchodilator spirometry will be performed.
- If eligible based on S0 data, participants will undergo baseline bronchoscopy with bronchoalveolar lavage (BAL) for collection of lung cathelicidin levels (visit B1). Blood for cathelicidin, vitamin D binding protein, vitamin D and PBMC will be collected at this visit.
- They will then return to the SPIROMICS research clinic weekly for eight weeks of directly observed vitamin D supplementation as well as assessment of adverse events (visits V0-V7).
 - After the initial four weeks of treatment (V4), all patients will be evaluated and have blood work obtained for calcium level to monitor for hypercalcemia.
 - Patients will be screened at each weekly visit for symptoms of hypercalcemia.
- After 8 weeks of vitamin D treatment, serum 25OH-VitD levels will be measured (visit V8) to ensure increased level prior to undergoing bronchoscopy. Individuals not increasing vitamin D > 20 after 8 weeks will not be eligible for B2 bronchoscopy and will be deemed to have completed study. Blood for BMP/ calcium level will also be collected.
- A second BAL collection will occur after the eight week of vitamin D treatment to measure cathelicidin in the plasma and the BAL (visit B2). Blood for cathelicidin, vitamin D binding protein, vitamin D and PBMC will also be collected at this visit.
- All procedures will be research related. A visit window of ± 1 day is acceptable for all study visits except B1 and B2, where a 28 day window is permissible given potential delay in laboratory results and bronchoscopy scheduling.

Table. Study Data Collection Schedule

Visit	S0	B1	V0	V1	V2	V3	V4	V5	V6	V7	V8	B2
Time (weeks)	-2	-1	0	1	2	3	4	5	6	7	8	9
Window (+/- days)	0	28	1	1	1	1	1	1	1	1	1	28
Visit Duration (hrs)	2	5	1	0.5	0.5	0.5	1	0.5	0.5	0.5	1	5
Informed Consent	•											
Spirometry	•											
Vitamin D	•						•				•	
Vit D binding prot/cathelicidin/ PBMC		•										•
BMP/ calcium	•						•				•	
BAL		•										•
Drug administration			•	•	•	•	•	•	•	•		
Adverse events & interval history				•	•	•	•	•	•	•	•	

Key: Time= nominal visit time; S=screening visit, Bn= Bronchoscopy visit n, Vn=Study visit

SECTION 2: RECRUITMENT

2.1 Definition of Recruitment & Consent: Recruitment is establishing eligibility of the potential candidate and informing the candidate of their eligibility and signing of the informed consent form by the potential candidate.

2.2 Sources of Recruitment: Participants of the SPIROMICS study (Protocol NA_00035701- PI [name]) additional approved studies including prior COPD studies NA_00009880, NA_00035381, NA_00085617, NA_00068035, and IRB00047215. Total goal N=20. Recruitment happens at the Bayview Lung Health Study (SPIROMICS)

2.3 Process of Recruitment: Study team members from this protocol will receive a list of research participants from the above listed protocols who have previously indicated willingness to be contacted for future studies. This study team will contact research participants. These contacts will be made via phone call or in face-to-face encounters during scheduled study visits for the ongoing approved protocols. For recruitment via face-to-face encounter, these conversations will occur in a private office with a trained study team member.

2.4 Study Inclusion and Exclusion Criteria:

- i. Inclusion
 - i. Post-BD FEV1/FVC<0.70
 - ii. Post-BD FEV1> 50% predicted
 - iii. Age 18-80
 - iv. Current or former smokers
 - v. Serum calcium<10.5mg/dl
 - vi. 25-OH VitD<20 ng/ml at screening
 1. Note that target recruitment is at least 10 participants with 25-OH VitD <10 ng/ml
 - vii. CrCl \geq 60 mL/min as estimated by the Cockcroft-Gault equation
 - viii. Women of reproductive potential with negative serum or urine pregnancy test and be willing to refrain from participating in a conception process and subject/partner must use at least 2 reliable forms of contraceptives for the duration of the study
- ii. Exclusion
 - i. Current use of vitamin D supplements
 - ii. Oxygen use >2L/min at rest
 - iii. Known allergy/sensitivity or any hypersensitivity to components of study drugs or their formulations
 - iv. Pregnancy or currently breast-feeding
 - v. History of nephrolithiasis (kidney stones)
 - vi. Self-reported HIV positive serostatus
 - vii. Any condition that, in the opinion of the site investigator, would compromise the subject's ability to participate in the study.

SECTION 3: DETAILED STUDY VISIT PROCEDURES

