- If eligible based on S0 data, participants will undergo baseline bronchoscopy with bronchoalveolar lavage (BAL) for collection of lung cathelicidin levels (visit B1). Blood for cathelicidin, vitamin D binding protein, vitamin D and PBMC will be collected at this visit.
- They will then return to the Meadowmont research clinic weekly for eight weeks of directly observed vitamin D supplementation as well as assessment of adverse events (visits V0-V7).
 - After the initial four weeks of treatment (V4), all patients will be evaluated and have blood work obtained for calcium level to monitor for hypercalcemia.
 - Patients will be screened at each weekly visit for symptoms of hypercalcemia.
- After 8 weeks of vitamin D treatment, serum 25OH-VitD levels will be measured (visit V8) to ensure increased level prior to undergoing bronchoscopy. Individuals not increasing vitamin D > 20 after 8 weeks will not be eligible for B2 bronchoscopy and will be deemed to have completed study. Blood for BMP/ calcium level will also be collected.
- A second BAL collection will occur after the eight week of vitamin D treatment to measure cathelicidin in the plasma and the BAL (visit B2). Blood for cathelicidin, vitamin D binding protein, vitamin D and PBMC will also be collected at this visit.
- A 24 hour post-bronchoscopy follow-up phone call will occur after B1 and B2
- All procedures will be research related. A visit window of ± 1 day is acceptable for all study visits except B1 and B2, where a 28 day window is permissible given potential delay in laboratory results and bronchoscopy scheduling.

Table. Study Data Collection Schedule

Visit	S0	B1	V0	V1	V2	V3	V4	V5	V6	V7	V8	B2
Time (weeks)	-2	-1	0	1	2	3	4	5	6	7	8	9
Window (+/- days)	0	28	1	1	1	1	1	1	1	1	1	28
Visit Duration (hrs)	2	5	1	0.5	0.5	0.5	1	0.5	0.5	0.5	1	5
Informed Consent	•											
Spirometry	•											
Vitamin D	•						•				•	
Vit D binding prot/cathelicidin	•										•	

PBMC		•									•
BMP/ calcium	•						•			•	
BAL		•									•
Drug administration			•	•	•	•	•	•	•	•	
Adverse events & interval history				•	•	•	•	•	•	•	

Key: Time= nominal visit time; S=screening visit, Bn= Bronchoscopy visit n, Vn=Study visit

SECTION 2: RECRUITMENT

2.1 Definition of Recruitment & Consent: Recruitment is establishing eligibility of the potential candidate and informing the candidate of their eligibility and signing of the informed consent form by the potential candidate.

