3.6 Bronchoscopy (B2)

- i. The target windows for scheduling the bronchoscopy is 1 week after V8 for the second procedure.
- ii. On day of bronchoscopy, the following blood will be obtained (processed at [name] lab):
 - a. Two 10 ml Green Top Lithium tubes for PBMC storage

See “**BRONCHOSCOPY PROCEDURES**” for procedure details

SECTION 4: REPORTING EVENTS

The proposed intervention study involves treatment of participants with vitamin D with the goal of determining if this intervention is efficacious in altering lung cathelicidin levels, and is therefore classified as a clinical trial. Because this is a clinical trial, the PI will designate an independent monitor to perform independent review of ongoing study progress and safety. Adverse events (AE) will be reported both to our IRB and the Independent Monitor through annual progress reports or more frequently as described below. AE reports and annual summaries will not include subject- or group-identifiable material. Each report will only include the identification code.

The Independent Monitor for this study is [name] at Johns Hopkins ([contact])

For this application, an adverse event is defined as any untoward medical occurrence in a subject during participation in the clinical study or with use of the intervention (vitamin D) being studied. An adverse finding can include a sign, symptom, abnormal assessment (laboratory test value, vital signs, etc.), or any combination of these. A serious adverse event (SAE) is any adverse event that results in one or more of the following outcomes:

- Death
- A life-threatening event
- Inpatient hospitalization or prolongation of existing hospitalization
- A persistent or significant disability/incapacity
- A congenital anomaly or birth defect
- An important medical event based upon appropriate medical judgment

AEs will be labeled according to severity, which is based on their impact on the patient. An AE will be termed “mild” if it does not have a major impact on the patient, “moderate” if it causes the patient some minor inconvenience, and “severe” if it causes a substantial disruption to the patient’s well-being. AEs will be categorized according to the likelihood that they are related to the study intervention. Specifically, they will be labeled definitely unrelated, definitely related, probably related, or possibly related to the study intervention.

The PI will review AE rates at least monthly.

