AEs will be labeled according to severity, which is based on their impact on the patient. An AE will be termed “mild” if it does not have a major impact on the patient, “moderate” if it causes the patient some minor inconvenience, and “severe” if it causes a substantial disruption to the patient’s well-being. AEs will be categorized according to the likelihood that they are related to the study intervention. Specifically, they will be labeled definitely unrelated, definitely related, probably related, or possibly related to the study intervention.

The PI and Independent monitor will review AE rates at least monthly.

When an AE occurs, the AE will be reported to the Institutional Review Board at Johns Hopkins Hospital and Bloomberg School of Hygiene, to the funding agency and to the Independent Monitor. Our procedure is for the study coordinator to notify the Principal Investigators and for the program staff to make necessary arrangements for the participant to see a medical provider. Most assessments will occur in research space adjacent to the Hopkins clinics, and referrals would be made to the clinic acute provider. The Johns Hopkins Emergency Room is the first choice for emergent care, and we would arrange for transport or accompany the participant as needed. SAEs that are unanticipated, serious, and possibly related to the study intervention will be reported to the Independent Monitor and IRB in accordance with requirements.

Unexpected fatal or life-threatening AEs related to the intervention will be reported to the IRB and Independent Monitor within 3 days. Other serious and unexpected AEs related to the

intervention will be reported to the IRB and Independent Monitor within 14 days. Anticipated or unrelated SAEs will be handled in a less urgent manner but will be reported to the Independent Monitor and IRB. In the annual AE summary, the Independent Monitor Report will be required to state that they have reviewed all AE reports.

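### The mild and moderate adverse event grades overlap and laboratory findings have no value-based grade, so symptom-free hypercalcemia of any size can be labelled mild

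*Protocol*

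**What the plan says.** The UNC and SPIROMICS/Bayview protocols carry the same severity scale in Section 4 (Reporting Events).

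- **Basis of grading:** "AEs will be labeled according to severity, which is based on their impact on the patient". No other basis is given.
- **Mild and moderate:** an event is mild "if it does not have a major impact on the patient, “moderate” if it causes the patient some minor inconvenience".
- **Severe:** "if it causes a substantial disruption to the patient’s well-being".
- **What counts as an adverse finding:** "An adverse finding can include a sign, symptom, abnormal assessment (laboratory test value, vital signs, etc.), or any combination of these". A laboratory result can therefore be an adverse event without any symptom.

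Section 1.4 of both protocols has participants evaluated at V4 and "blood work obtained for calcium level to monitor for hypercalcemia"; calcium is measured again at V8. Participants are also asked about symptoms of hypercalcemia at each weekly visit. The only calcium cut-off in either protocol is the entry criterion of less than 10.5 mg/dl in Section 2.4, which is not a severity grade. The SAP contains no adverse event analysis.

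**The concern.** A severity scale is useful if two people applying it to the same event reach the same grade. Here the wording for mild takes in everything described by the wording for moderate, and no rule settles which label wins. This affects ordinary events. Section 8 lists sore throat, coughing and nose-bleed among the bronchoscopy risks, and each could reasonably be called a minor inconvenience without major impact.

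The second weakness concerns laboratory findings. The V4 and V8 blood tests can detect a raised calcium that the weekly symptom questions would miss. Such a finding may have no felt impact, and impact is the only thing the scale measures. The size of the abnormality does not enter the grade.

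What is at stake is the safety record. Adverse events go to the IRB, the funder and the Independent Monitor. The Annual Report must list and summarise them, compare their rates with pre-study assumptions and address whether continuing is justified. With 20 participants planned per site, a few inconsistently graded events could alter the severity profile those readers see.

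**Working it through.** The plan gives no figure to reproduce. The check asks whether the three definitions are mutually exclusive, whether they rise in order, and whether any text grades a laboratory result by its value.

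**Step 1: each level of impact against each definition (Section 4, both protocols).**

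| Impact of the event | Meets mild? | Meets moderate? | Meets severe? |
|---|---|---|---|
| None felt | Yes | Not by itself | No |
| Minor inconvenience | Yes | Yes | No |
| More than minor, less than major | Yes | Depends on reading | No |
| Substantial disruption | No, if substantial means major | Depends on reading | Yes |

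The second row is the defect: one event satisfies two grades under any ordinary reading. In the last two rows the moderate entry turns on whether the term is a band (only a minor inconvenience) or a threshold (at least a minor inconvenience). The text does not say. Nor does it say whether major and substantial mean the same thing.

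**Step 2: laboratory findings.** Three statements are combined. An abnormal laboratory value can be an adverse event. Severity rests on impact on the patient. No section grades calcium, or any other result, by size. It follows that two symptom-free calcium results of very different size can both meet the mild definition.

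**Step 3: whether mild is the only possible label for such a result.** It is not. Section 4 has staff arrange for a participant with an adverse event to see a provider. That visit, or a repeat blood draw, could be called a minor inconvenience, which gives moderate. An admission could be called a substantial disruption, which gives severe, and it would also meet the definition of a serious event. The conclusion is therefore *can be* graded mild, not *is* graded mild.

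**Step 4: where the grade is used.** The Section 4 reporting times of 3 and 14 days depend on whether the event is serious (or fatal or life-threatening), unexpected and related. The severity label does not enter. No stopping step or SAP analysis uses it. It matters only as a descriptor in reports and summaries.

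**Step 5: opportunities for the problem to arise.** With 20 participants planned per site:

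- calcium tests after the start of treatment (V4, V8): 20 × 2 = 40 per site at most;
- adverse events forms (V1 to V8): 20 × 8 = 160 per site at most.

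These are upper bounds on occasions for grading, assuming full attendance. They do not predict how many events will occur or be misgraded.

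**The case against.** The strongest reply is that the label drives nothing. Every adverse event goes to the IRB, the funder and the Independent Monitor whatever its grade. The Monitor must confirm having reviewed all the reports, and the Annual Report contains a list as well as a summary. V4 and V8 results go to the study physician regardless of label, and a marked calcium rise can be made a serious event under the important-medical-event criterion. Each protocol is single-arm, so no comparison between arms is biased. All of this stands. It confines the harm to the labels and leaves detection and expedited reporting intact.

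Four stronger readings are tempting, and the documents do not support them:

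- **That symptom-free hypercalcemia is always graded mild.** The scale refers to impact, not symptoms, and follow-up care can itself be an impact. The overlap also means that nothing is fixed as mild.
- **That an event worse than a minor inconvenience necessarily drops back to mild, below a lesser event.** This follows only if moderate is read as a band. If the terms are rising thresholds and the highest one met is used, the order is sound. That rule is not written, but the opposite is not written either.
- **That calcium is the only laboratory safety monitoring.** V4 and V8 draw a full basic metabolic panel and 25-OH vitamin D.
- **That two coordinators would grade differently.** Section 4 does not say who assigns severity; the coordinator's stated role is to notify the investigators.

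Finally, Section 6 (study forms) is listed but not shown. The adverse events form may already carry finer grades. If so, Section 4 should refer to them, because as it stands it states the definitions itself.

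**Conclusion.** The point holds in limited form. In both protocols an event of minor inconvenience meets the mild and the moderate definition with no tie-break, and a laboratory abnormality is graded without regard to its size. Symptom-free hypercalcemia of any size found at V4 or V8 can therefore be labelled mild.

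This is a defect in a stated rule rather than a missing detail, and it is worth correcting. Its effect is on the consistency and interpretability of severity labels. A reader might infer that the safety data as a whole cannot be interpreted, or that serious toxicity would go unreported. Neither follows, since the events themselves are listed and reported by routes that do not use the grade.

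The conclusion assumes that a minor inconvenience is by ordinary meaning not a major impact, and that the unseen adverse events form does not already resolve the overlap or grade laboratory values. The number of events affected is unknown.

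**What to change.** In Section 4 of both protocols, and in the adverse events form if it does not already do so:

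1. Replace the three definitions with mutually exclusive, ordered grades that also cover findings the participant does not notice. For example: mild, no interference with usual activity; moderate, some interference short of substantial disruption; severe, substantial disruption.
2. State that the highest grade met is assigned.
3. Grade laboratory adverse events by measured value on a laboratory toxicity scale named in the protocol. The choice of scale and its cut-offs is a clinical matter for the sponsor.

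The cost is a few sentences in each protocol and, if needed, a revised form. Treatment, eligibility and the primary analysis are untouched. Events already recorded could be regraded from the forms and stored laboratory values, provided those hold enough detail. The downside is that some events may be graded higher than under the present text, so summaries before and after the change should not be pooled without regrading.

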When an AE occurs, the AE will be reported to the Institutional Review Board at UNC, to the funding agency and to the Independent Monitor. Our procedure is for the study coordinator to notify the Principal Investigators and for the program staff to make necessary arrangements for the participant to see a medical provider. Most assessments will occur in research space adjacent to the Meadowmont clinic, and referrals would be made to the clinic acute provider. The Emergency Room is the first choice for emergent care, and we would arrange for transport or accompany the participant as needed. SAEs that are unanticipated, serious, and possibly related to the study intervention will be reported to the Independent Monitor and IRB in accordance with requirements.

Unexpected fatal or life-threatening AEs related to the intervention will be reported to the IRB and Independent Monitor within 3 days. Other serious and unexpected AEs related to the

intervention will be reported to the IRB and Independent Monitor within 14 days. Anticipated or unrelated SAEs will be handled in a less urgent manner but will be reported to the Independent Monitor and IRB. In the annual AE summary, the Independent Monitor Report will be required to state that they have reviewed all AE reports.

Study progress and safety will be reviewed monthly by the PI. Progress reports, including patient recruitment, retention/attrition, and AEs, will be provided to the Independent Monitor annually. An Annual Report will be compiled and will include a list and summary of AEs. In addition, the Annual Report will address (1) whether AE rates are consistent with pre-study assumptions; (2) reason for dropouts from the study; (3) whether all participants met entry criteria; (4) whether continuation of the study is justified on the basis that additional data are needed to accomplish the stated aims of the study; and (5) conditions whereby the study might be terminated prematurely. The Annual Report will be sent to the Independent and included in the Progress Report to the NIH. The IRB and other applicable recipients will review progress of this study on an annual basis.

During the funding of this study, any action by the IRB, the Independent Monitor, or one of the study investigators that results in a temporary or permanent suspension of the study will be reported to the NHLBI Program Official within 1 business day of notification.

SECTION 5: STUDY VISIT CHECKLISTS

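### Section 4 ties the 3-day and 14-day reporting deadlines to vitamin D alone, so an unexpected serious event caused by a research bronchoscopy has no deadline stated in the protocol; the adverse event form is also on neither bronchoscopy checklist

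*Protocol*

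**What the plan says.** Section 4 (Reporting Events) reads almost identically in the two supplied protocols. Its definition of an adverse event covers anything untoward during participation, or "with use of the intervention (vitamin D) being studied". Causality is then judged against that intervention only: "AEs will be categorized according to the likelihood that they are related to the study intervention".

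The reporting rules are:

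- A general duty with no interval. At UNC: "When an AE occurs, the AE will be reported to the Institutional Review Board at UNC", and also to the funder and the Independent Monitor. Bayview has the equivalent for its own IRB.
- A sentence limited to possibly related events: "SAEs that are unanticipated, serious, and possibly related to the study intervention will be reported" to the monitor and IRB, as requirements dictate.
- The 3-day rule: "Unexpected fatal or life-threatening AEs related to the intervention will be reported to the IRB and Independent Monitor within 3 days".
- A rule for other serious, unexpected events, again only those related to the intervention: "intervention will be reported to the IRB and Independent Monitor within 14 days".
- A residual rule: "Anticipated or unrelated SAEs will be handled in a less urgent manner but will be reported to the Independent Monitor and IRB".

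On collection, Section 3.5 and the Section 5 checklists put the adverse event form at V1 to V8 at both sites. It is absent from the V0, B1 and B2 checklists. The overview in Section 1.4 mentions assessment at V0 to V7. UNC's Section 1.4 also plans a telephone call 24 hours after each bronchoscopy; the Bayview v1.7 text has no such call.

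**The concern.** The bronchoscopies are the most invasive thing done to participants. They involve sedation, and Section 8 says participants are to be told that they are for research and not for care. Section 8 also lists their risks, including sedation reactions and infection. Section 4 never mentions them.

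Followed exactly, the plan gives the monitor and IRB a dated report of an unexpected serious event if it is attributed to vitamin D, and an undated one if the same event is attributed to the procedure. The checklists that staff work through do not prompt an adverse event record at either bronchoscopy, and nothing prompts one after the second. What is at stake is the timeliness and completeness of safety oversight, not the cathelicidin comparison.

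**Working it through.** No statistical figure is involved. The check compares the passages and adds up visit intervals.

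**1. How the same unexpected event is sorted (Section 4, both protocols)**

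| Event | Related to vitamin D | Caused only by bronchoscopy, lavage or sedation |
|---|---|---|
| Fatal or life-threatening | 3 days | Must be reported; no interval stated |
| Other serious | 14 days | Must be reported; no interval stated |

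The sentence that defers to outside requirements does not fill the right-hand column, because it too is confined to events possibly related to the intervention.

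**2. When the gap applies**

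- B1 is nominally at week -1 and the first dose is at V0, week 0. An event between them cannot be related to vitamin D, so neither deadline can apply.
- B2 is nominally at week 9, after eight doses (V0 to V7). The relatedness scale has four labels, and only one of them (definitely unrelated) is a non-related label. A doubtful B2 event would therefore be labelled at least possibly related. The gap after B2 is limited to events judged definitely unrelated to vitamin D.

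**3. Periodic review as a substitute**

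- UNC: "The PI will review AE rates at least monthly", with progress reports to the monitor annually.
- Bayview v1.7: the monitor joins the monthly review of rates and receives progress reports after quarterly reviews.

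Neither is a time limit for an individual event.

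**4. Where the form falls around the bronchoscopies (Section 5)**

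- Form on the B1 and B2 checklists: 0 of 4 (two visits at two sites).
- B1 to V0 is 7 ± 1 days and V0 to V1 is 7 ± 1 days. The first form after B1 is at V1: 7 + 7 = 14 days nominally, from 6 + 6 = 12 to 8 + 8 = 16. If the one-week limit on V0 is only a maximum, 16 stands and the lower end is not fixed.
- The last form is at V8 (week 8), one week before B2 (week 9). Forms scheduled after B2: none.

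**5. Overview against forms**

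V0 to V7 and V1 to V8 are eight visits each. They share V1 to V7 (seven) and differ on V0 and V8 (two). The legible Bayview schedule table agrees with V1 to V8. The UNC table is broken in the text supplied and was not used.

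**The case against.** The strongest reply is that procedure events are adverse events under the protocol's own definition and must be reported when they occur. Only a number of days is missing, and the IRBs' rules may supply one. That is right. A reader might infer that bronchoscopy complications go unreported or that no deadline exists anywhere, and the documents support neither inference.

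Other readings also go too far:

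- **Bronchoscopy events go unrecorded, or nobody asks about them for two weeks.** The 14-day figure concerns the adverse event form only. UNC plans a 24-hour call. Section 8 at both sites requires supervised recovery and tells participants to contact the clinic or study physician about worrying symptoms. A physician completes a bronchoscopy form whose content was not supplied. These are real but partial safeguards. None is tied to the adverse event form, and the content of the call is not stated.
- **Two rival collection schedules make the adverse event rates uncertain.** Section 5 makes the checklists mandatory for each visit, and they agree with Section 3.5. The V0 to V7 reference is one parenthesis in an overview bullet that also covers dosing, so it is an editorial mismatch.
- **The share of bronchoscopies done before the first dose measures the harm.** It counts procedures, not serious events, and the documents give no event rate.
- **Every serious procedure event lacks a deadline because of the vitamin D wording.** Section 4 has a separate category for anticipated events. A listed procedure risk might fall there whatever the relatedness wording, so the point concerns unexpected events.

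Finally, the Bayview text is v1.7 of April 2016, while the SAP cites a COPD protocol dated 8/23/17 that was not supplied. Every Bayview statement here is subject to that check.

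**Conclusion.** The point holds in this form. In the supplied protocols, an unexpected serious event caused by a research procedure is classed as unrelated and has no reporting deadline stated in the protocol, where the same event attributed to vitamin D has 3 or 14 days. The resulting delay cannot be computed, because the general duty to report carries no interval.

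The gap is clean between B1 and V0 and partial after B2. Alongside it, the adverse event form is missing from all four bronchoscopy checklists and is not scheduled after B2.

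This is a worthwhile correction to safety oversight; the primary analysis does not depend on it. The conclusion assumes that Section 4 means what its parenthesis says by intervention, that the 8/23/17 COPD protocol does not already differ, and that neither the Section 6 forms nor the IRBs' rules close the gap. None of those documents was supplied.

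**What to change.** 1. In Section 4, extend the possibly-related sentence and the 3-day and 14-day sentences to events related to the intervention or to a study procedure (bronchoscopy, lavage, sedation). Record relatedness to vitamin D and to study procedure as two items on the existing four-level scale, so that unrelated means unrelated to both.
2. Add the existing adverse event form to the B1 and B2 checklists and to UNC's planned 24-hour call, and list that call on the checklists, so that events after B2 are recorded.
3. Reconcile the V0 to V7 overview wording with the V1 to V8 forms. Check the 8/23/17 COPD protocol before editing the Bayview text, including whether it has a post-bronchoscopy call.

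Cost per protocol: three sentence edits, one extra relatedness item, one corrected visit range, and one line on each of two bronchoscopy checklists (four lines over both sites). UNC also needs its call listed on the checklists; the call itself is already planned. The downside is slightly more expedited reports and a few more form lines.
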